## 12.9. Transfer of patients' data outside the European Union

The study performance entails transferring patients' personal data (coded pseudonymized data)

outside the EU. To this extent, the Sponsor, the Site, the Investigator, the Central Lab and the CRO, undertake to export such data in compliance with adequate safeguards/legal basis as required by the Regulation 679/2016 including the Commission Decisions, the Standard Contract Clauses, the Privacy Shield, patients' specific consent. The updated list of foreign countries is available upon request.

### **12.10. Exercise of patients' data privacy rights**

Each study patient has the right to contact the Sponsor, the Site, the Investigator, the Central Lab and the CRO to exercise the rights afforded to the patient by the law, including the afforded ones under articles 15 to 22 of Regulation (EU) 2016/679, as from time to time applicable and compatible with the study. Namely: knowing whether or not any data referring to his/her is being processed in the context of the study; access his/her data; verify the data's content, origin, exactness, location (including, where applicable, the non EU countries where the data might be); obtain a copy of the data including their transmission to another entity indicated by the patient; ask that the data are supplemented, updated, amended; in the circumstances set forth by the law, ask that the processing of data is restricted, that data are anonymised or frozen; oppose to the processing of his/her data for legitimate reasons. Each patient has the right to lodge a complaint with his/her local supervisory authority and/or to notify to the Data Protection Officer any use of his/her personal data the patient regards as inappropriate.

Each study patient is free to withdraw at any time from the study. In such case, each study patient may ask the Sponsor, the Site, the Investigator, the Central Lab and the CRO to destroy/delete his/her personal data including his/her biological samples, unless they have been permanently anonymised, thus preventing any further processing or analysis of his/her data. However, data and results of tests that may have been used to determine the results of the study shall not be deleted, to avoid altering or impairing altogether the results of the study. Please refer to [Section 12.8](#).

If the Site, the Investigator, the Central Lab and the CRO receives a request for data privacy rights exercise, the concerned recipient shall immediately inform the Sponsor DPO by email at [[contact]](mailto:[contact])

The request shall be fulfilled within the term set forth by the applicable privacy laws (normally 30 days). The Sponsor, the Site, and the Investigator, the Central Lab and the CRO shall implement adequate organisational measures to reply to patients within the above mentioned deadline.

### **12.11. Future research**

Upon IRB/IECs and regulatory agencies approvals received, with patients' optional and additional consent, the Sponsor and/or the Site may use the data collected during the course of the study for further medical and scientific research purposes. These may include, for example: retrospective clinical studies; clinical studies pertaining to the patients' pathology/medical condition(s) or similar conditions; studies which compare the data of this Study with those from other sources to identify the factors involved in a disease; registration of new medicines.

In the context of these additional research activities, patients' data will be processed, pseudonymised and transferred abroad and may be shared with future research partners.

### 13. END OF CLINICAL TRIAL AND ARCHIVING

The study will end with the collection and analysis of study data and the issue of the clinical study report. All essential documents will be archived by the Sponsor according to the relevant SOP.

#### 13.1. Archiving Of Electronic Documentation/Data

As described in Section 12.5, duplicate electronic media such as CDs/DVDs (1 for routine access and 1 for back-up) containing the patient data in PDF format (i.e., eCRFs) for each site will be prepared by the Sponsor or a delegate for archiving purposes. The electronic media, of not re-printable type, will be appropriately labelled recording the files/data included. The files should contain at least the eData copy clearly reporting the system name, study code and the eCRF version used; for eCRF data also the electronic signature and the associated audit trails have to be included. The Investigator should verify whether the provided electronic media represent a complete copy of eCRFs generated during the study. The Investigator has to confirm the receipt and correctness of the material by signing a dedicate form provided by the Sponsor, the signed form has to be collected and archived in the TMF. Investigators will be also responsible for electronic media refreshment approximately every 7 years to ensure long term archiving of files/data. Two copies of the same electronic media prepared for the sites or cumulative electronic media with the same content will be archived by the Sponsor and refreshed approximately every 7 years to ensure long term archiving of files/data. In addition the Sponsor is responsible to create 2 electronic media (1 for routine access and 1 for back-up) containing an integrated SAS database with all study data (e.g., eCRF, central laboratory), with appropriate refreshment procedures.

## APPENDIX A: EASTERN COOPERATIVE ONCOLOGY GROUP PERFORMANCE SCORE

Grade	ECOG Performance Score 
0	Fully active. Able to carry on all pre-disease performance without restriction.
1	Restricted in physically strenuous activity but ambulatory and able to carry out work of a light or sedentary nature (e.g. light house work, office work).
2	Ambulatory and capable of all self-care but unable to carry out any work activities. Up and about more than 50% of waking hours.
3	Capable of only limited self-care, confined to bed or chair more than 50% of waking hours.
4	Completely disabled. Cannot carry on any self-care. Totally confined to bed or chair.
5	Dead.

**APPENDIX B: CREATININE CLEARANCE ALGORITHM**

Creatinine clearance should be calculated using the Cockcroft-Gault Formula, which is given below:

$$\text{CrCl} = \frac{(140 - \text{Age}) \times \text{Mass (in kilograms)} \times (0.85 \text{ if Female})}{72 \times \text{serum Creatinine (in mg/dL)}}$$

## APPENDIX C: SUPPORTING INFORMATION FOR ASSESSMENT OF ADVERSE EVENTS

National Cancer Institute Common Terminology Criteria for Adverse Events (NCI CTCAE) v4.03 can be found at the website of the National Cancer Institute.

<http://evs.nci.nih.gov/ftp1/CTCAE>

The following table provides supporting information to assess the relationship of AEs with study (test) drug.

1	Not related	This category applies to those adverse events which, after careful consideration, are clearly and incontrovertibly due to extraneous causes (disease, environment, etc.).
2	Unlikely (must have two)	In general, this category can be considered applicable to those adverse events which, after careful medical consideration at the time they are evaluated, are judged to be unrelated to the test drug. An adverse event may be considered unlikely if or when: 
 
1. It does not follow a reasonable temporal sequence from administration of the test drug.
 
2. It could readily have been produced by the patient's clinical state, environmental or toxic factors, or other modes of therapy administered to the patient.
 
3. It does not follow a known pattern of response to the test drug.
 
4. It does not reappear or worsen when the drug is readministered.
 

3	Possibly (must have two)	This category applies to those adverse events for which, after careful medical consideration at the time they are evaluated, a connection with the test drug administration appears unlikely but cannot be ruled out with certainty. An adverse event may be considered possibly related if or when: 
 
1. It follows a reasonable temporal sequence from administration of the test drug.
 
2. It could not readily have been produced by the patient's clinical state, environmental or toxic factors, or other modes of therapy administered to the patient.
 
3. It follows a known pattern of response to the test drug.
 

4	Probably (must have three)	This category applies to those adverse events for which, after careful medical consideration at the time they are evaluated, are felt with a high degree of certainty to be related to the test drug. An adverse event may be considered probably related if or when: 
 
1. It follows a reasonable temporal sequence from administration of the test drug.
 
2. It could not be reasonably explained by the known characteristics of the patient's clinical state, environmental or toxic factors, or other modes of therapy administered to the patient.
 
3. It disappears or decreases on cessation or reduction in dose. There are important exceptions when an adverse event does not disappear upon discontinuation of the drug, yet drug-relatedness clearly exists (e.g., bone marrow depression, fixed drug eruptions, tardive dyskinesia).
 
4. It follows a known pattern of response to the test drug.
 

5	Definitely (must have all)	This category applies to those adverse events which, the Investigator feels are incontrovertibly related to test drug. An adverse event may be assigned an attribution of definitely related if or when: 
 
1. It follows a reasonable temporal sequence from administration of the test drug.
 
2. It could not be reasonably explained by the known characteristics of the patient's clinical state, environmental or toxic factors, or other modes of therapy administered to the patient.
 
3. It disappears or decreases on cessation or reduction in dose with re-exposure to drug. (Note: this is not to be construed as requiring re-exposure of the patient, however, a category of definitely related can only be used when a recurrence is observed.)
 
4. It follows a known pattern of response to the test drug.
 

## APPENDIX D: AML RESPONSE CRITERIA

Category	Definition	Comment
Response#		
CR without minimal residual disease (CR MRD -)	If studied pretreatment, CR with negativity for a genetic marker by RT-qPCR, or CR with negativity by MFC	Sensitivities vary by marker tested, and by method used; therefore, test used and sensitivity of the assay should be reported; analyses should be done in experienced laboratories (centralized diagnostics)
Complete remission (CR)	Bone marrow blasts <5%; absence of circulating blasts and blasts with Auer rods; absence of extramedullary disease; ANC $\geq 1.0 \times 10^9/L$ (1000/ $\mu$ L); platelet count $\geq 100 \times 10^9/L$ (100 000/ $\mu$ L)	MRD + or unknown
CR with incomplete hematologic recovery (CRi)	Bone marrow blasts <5%; absence of circulating blasts and blasts with Auer rods; absence of extramedullary disease with incomplete recovery of peripheral blood counts (ANC < $1.0 \times 10^9/L$ [1000/ $\mu$ L] or platelet count < $100 \times 10^9/L$ [100 000/ $\mu$ L])	
CR with partial hematologic recovery (CRh) 	Bone marrow blasts <5%; absence of circulating blasts and blasts with Auer rods; absence of extramedullary disease with partial recovery of peripheral blood counts (ANC > $0.5 \times 10^9/L$ [500/ $\mu$ L] and platelet count > $50 \times 10^9/L$ [50 000/ $\mu$ L])	
Morphologic leukemia-free state (MLFS)	Bone marrow blasts <5%; absence of blasts with Auer rods; absence of extramedullary disease; no hematologic recovery required	Marrow should not merely be “aplastic”; at least 200 cells should be enumerated or cellularity should be at least 10%
Partial remission (PR)	All hematologic criteria of CR; decrease of bone marrow blast percentage to 5% to 25%; and decrease of pretreatment bone marrow blast percentage by at least 50%	Especially important in the context of phase 1-2 clinical trials
Treatment failure		

Primary refractory disease	No CR or CR i after 2 courses of intensive induction treatment; excluding patients with death in aplasia or death due to indeterminate cause	Regimens containing higher doses of cytarabine are generally considered as the best option for patients not responding to a first cycle of 7+3; the likelihood of responding to such regimens is lower after failure of a first
Death in aplasia	Deaths occurring $\geq 7$ d following completion of initial treatment while cytopenic; with an aplastic or hypoplastic bone marrow obtained within 7 d of death, without evidence of persistent leukemia	
Death from indeterminate cause	Deaths occurring before completion of therapy, or $<7$ d following its completion; or deaths occurring $\geq 7$ d following completion of initial therapy with no blasts in the blood, but no bone marrow examination available	
Response criteria for clinical trials only		
Stable disease	Absence of CR MRD -, CR, CR i , PR, MLFS; and criteria for PD not met	Period of stable disease should last at least 3 mo
Progressive disease (PD)*,†	
Evidence for an increase in bone marrow blast percentage and/or increase of absolute blast counts in the blood:
 
 
• <math>>50\%</math> increase in marrow blasts over baseline (a minimum 15% point increase is required in cases with <math><30\%</math> blasts at baseline; or persistent marrow blast percentage of <math>>70\%</math> over at least 3 mo; without at least a 100% improvement in ANC to an absolute level (<math>>0.5 \times 10^9/L</math> [<math>500/\mu L</math>], and/or platelet count to <math>>50 \times 10^9/L</math> [<math>50\,000/\mu L</math>] nontransfused); or
 
• <math>>50\%</math> increase in peripheral blasts (WBC <math>\times</math> % blasts) to <math>>25 \times 10^9/L</math> (<math>>25\,000/\mu L</math>) (in the absence of differentiation syndrome); or
 
	
Category mainly applies for older patient given low intensity or single-agent “targeted therapies” in clinical trials.
 
In general, at least 2 cycles of a novel agent should be administered. Some protocols may require blast increase in 2 consecutive marrow assessments at least 4 wk apart; the date of progression should then be defined as of the first observation date.
 
Some protocols may allow transient addition of hydroxyurea to lower blast counts.
 
“Progressive disease” is usually accompanied by a decline in ANC and platelets and increased transfusion requirement and decline in performance status or increase in symptoms.

	
 
• New extramedullary disease
 
	
Relapse		
Hematologic relapse (after CR MRD -, CR, CR i , CRh)	Bone marrow blasts $\geq 5\%$ ; or reappearance of blasts in the blood; or development of extramedullary disease	
Molecular relapse (after CR MRD -)	If studied pretreatment, reoccurrence of MRD as assessed by RT-qPCR or by MFC	Test applied, sensitivity of the assay, and cutoff values used must be reported; analyses should be done in experienced laboratories (centralized diagnostics)

Table adapted from Döhner H, *et al* 2017

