### 5.3.11. Disease evaluation

Evaluation of disease status will be performed at the time-points described in the Schedule of Study Assessment (Table 5), according to the AML Response Criteria in [Appendix D](#).

Disease assessment will involve evaluation of leukemic blast proportion in the bone marrow. Hematologic parameters from the routine local assessments including blast percentage (where applicable), platelet count, and other relevant parameters such as transfusion dependence will also contribute to this assessment.

To note, disease assessment must be performed as soon as the peripheral lab results become consistent with an objective response. Disease assessment will also include an aliquot of bone marrow aspirate/biopsy that will be centrally stored for future analysis (e.g. minimal residual disease), if any. In case bone marrow aspirate/biopsy is consistent with CRi or better response but still a minimal percentage of peripheral blasts is detected, the response assessment can be postponed up to 2 weeks and will be based on repeated peripheral blood results and last bone marrow aspiration results.

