## 6.9. Permitted and Restricted Concomitant Medications

Medications specifically prohibited in the exclusion criteria ([Section 3.2](#)) are not allowed during the ongoing study. If there is a clinical indication for any medication specifically prohibited during the study, discontinuation from study therapy may be required. The Investigator should discuss any questions regarding this with the assigned Medical Monitor for the study. The final decision on any supportive therapy or vaccination rests with the Investigator and/or the patient's primary physician. However, the decision to continue the patient on study treatment requires agreement from the Medical Monitor.

Note that use of erythropoiesis stimulating agents and growth factors during Cycle 1 is prohibited. Beyond Cycle 1, their use should be avoided; however, their use may be discussed with the Medical Monitor on a case-by-case basis.

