### 6.9.1. Acceptable concomitant medications

All treatments that the Investigator considers necessary for their patient's welfare may be administered at their discretion in keeping with the standards of medical care. All concomitant medication will be recorded on the eCRF including all prescription, over-the-counter, herbal supplements, pre-medications, intravenous medications or transfusions. Note that the assessment of red cell transfusions will be part of the disease assessment criteria (see [Section 5.3.11](#)). If changes occur during the study period, documentation of drug dosage, frequency, route, and date may also be included on the eCRF. All concomitant medications the patient received within 30 days before the first dose of SEL24/MEN1703 and 30 days after the last dose of SEL24/MEN1703 should be recorded. Concomitant medications administered after 30 days from the last dose of SEL24/MEN1703 should be recorded for SAEs and any Events of Clinical Interest (ECIs) as defined in [Section 7.10](#).

Sites should follow their institutional guidelines for treating hypophosphatemia, including administration of oral or I.V. phosphate supplements. Phosphate supplements should be started the same day any  $\geq$ Grade 3 hypophosphatemia is detected. Patients should be retested no less than every 24 hours, until phosphate levels are  $\leq$ Grade 2. SEL24/MEN1703 treatment may be reinstated per the retreatment guidelines provided in [Section 4.4](#). Lower grade abnormalities should be monitored and corrected as soon as possible. Additional assessments should be carried out as clinically indicated.

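### Response criteria do not say that the ANC and platelet counts behind CR, CRh and PR must be free of platelet transfusion or growth-factor support

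*Protocol*

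**What the plan says.** Protocol Appendix D defines CR as marrow blasts below 5%, then "absence of circulating blasts and blasts with Auer rods; absence of extramedullary disease; ANC" at least 1.0 and platelets at least 100 (both x10^9/L). CRh has the same marrow condition and "absence of extramedullary disease with partial recovery of peripheral blood counts", meaning ANC above 0.5 and platelets above 50. CRi has the same marrow condition with ANC below 1.0 or platelets below 100. PR takes over the CR counts: "All hematologic criteria of CR; decrease of bone marrow blast percentage to 5% to 25"%, with at least a 50% fall from the pretreatment level. None of these rows mentions transfusion or growth factor. The only such qualifier in the appendix is in the PD row, where the platelet improvement to above 50 must be "nontransfused".

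Protocol 5.3.11 says that "other relevant parameters such as transfusion dependence will also contribute to this assessment", without a window, threshold or consequence. The synopsis and SAP 5.4.2 and 12 use similar wording. Protocol 6.9.1 adds: "Note that the assessment of red cell transfusions will be part of the disease assessment criteria", pointing to 5.3.11. Under Protocol 6.9, growth factors are prohibited in Cycle 1. After that: "Beyond Cycle 1, their use should be avoided; however, their use may be discussed with the Medical Monitor on a case-by-case basis".

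SAP 12.1 refers back to Appendix D and adds no condition on counts. SAP 5.4.2 defines ORR as CR, CRi, CRh or MLFS and makes the PR rate a separate secondary endpoint.

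**The concern.** CR, CRh and CRi share the marrow condition and differ only in the blood counts, and PR depends on the CR counts. A platelet transfusion shortly before the sample, or growth factor in a later cycle, can lift a count over a threshold without marrow recovery. The label then partly reflects supportive care. The documents recognise this elsewhere: the PD row qualifies its platelet count, and the engraftment condition in Protocol 4.2 for resuming drug after transplant asks for counts without transfusion. The value 50 for platelets is thus qualified for PD and unqualified for CRh in one table.

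At stake are the best-response tabulation in SAP 12.1, including MRD-negative CR (which builds on CR), the PR rate, and any DoR whose starting response is PR. With about 20 patients per expansion cohort, one label is visible in the result.

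**Working it through.** The plan states no figure on this point, so there is none to reproduce. The check classifies example patients with and without an unsupported-count condition, then sizes one reclassification.

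**Inputs.** Thresholds from Appendix D; response sets from SAP 5.4.2 and 12.1; cohort sizes of about 20 (IDH mutants) and 23 (all-comers) from Protocol 8.13; exact 95% CI for Part 2 response from Protocol 8.9.

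**Can support coincide with a response assessment?** Yes. Transfusions are at the investigator's discretion (Protocol 6.9.1). Growth factor is possible after Cycle 1. The first post-baseline marrow may be as late as Cycle 3 Day 1 (footnote 7 of the schedule of assessments).

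**Classification.** The patients are hypothetical. All have supported counts and no circulating blasts. CRh is assumed to take precedence over CRi where both fit.

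| Marrow blasts | ANC | Platelets | As written | Unsupported counts required |
|---|---|---|---|---|
| 3% | 1.2 | 110 | CR | CRi |
| 3% | 0.7 | 60 | CRh | CRi |
| 15% (baseline 40%) | 1.2 | 110 | PR | not PR |

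The last column assumes that CRi is extended to take in such patients. As written, CRi needs a measured ANC below 1.0 or platelets below 100. The first patient has neither, so a bare unsupported-count condition would leave only MLFS.

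**Effect on each endpoint.**
- ORR: CR or CRh to CRi stays inside the set, and PR was never in it. No change.
- Best-response split, MRD-negative CR and PR rate: change by one patient each time.
- DoR: starts from CR, CRi, CRh, MRD-negative CR, MLFS or PR. A move to CRi keeps the start date; a lost PR removes or delays it.
- RFS and the EFS treatment-failure rule: both accept CRi but not MLFS. They are unchanged if the patient goes to CRi, but can change if the patient falls to MLFS.

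**Size.** Shift per patient = 100/n: 100/20 = 5.0 points; 100/23 = 4.3 points.

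Exact (Clopper-Pearson) limits for x of n are the 2.5% quantile of Beta(x, n-x+1) and the 97.5% quantile of Beta(x+1, n-x):

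| x/n | Rate | 95% CI |
|---|---|---|
| 1/20 | 5.0% | 0.1 to 24.9 |
| 2/20 | 10.0% | 1.2 to 31.7 |
| 1/23 | 4.3% | 0.1 to 21.9 |
| 2/23 | 8.7% | 1.1 to 28.0 |

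With counts this small, one label can double a category's rate, although the intervals overlap widely.

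**The case against.** Several points on the other side stand.

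- Protocol 6.9.1 names red cell transfusions, and red cells do not enter the ANC or platelet thresholds. A reader might infer that Appendix D contradicts 6.9.1. It does not: the relevant text is the broader mention of transfusion dependence in 5.3.11.
- That text tells the assessor to weigh transfusion dependence, so Appendix D does not work in isolation. What is missing is the rule for doing so.
- Growth-factor use after Cycle 1 is discouraged and goes to the Medical Monitor, and the PD row's qualifier covers transfusion only. This limb is weaker than the platelet one.
- The results are secondary and descriptive. CR and CRh rates are not named endpoints; they appear in the best-response tabulation.
- The synopsis says that transfusion-dependency information is collected from Version 12.0, when Part 1 and the all-comers cohort were already enrolled. Protocol 6.9.1 lists transfusions as concomitant medication, but whether earlier records carry usable dates cannot be seen.
- Appendix D is adapted from a published table. What the sources require cannot be checked here, so the point rests on the internal comparison alone.

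These limit the reach of the point but do not remove it. An instruction to consider transfusion dependence, with no window or consequence, does not stop a transfused platelet count from meeting a numeric threshold. The transfusion endpoints do not fill the gap either. Post-baseline independence needs one 56-day transfusion-free period unconnected to the response date, patients treated for more than 28 but fewer than 84 days are not evaluable, and SAP 12.1 restricts these rates to the IDH-mutants cohort.

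**Conclusion.** The gap is real and moderate in weight. As written, counts held up by platelet transfusion or growth factor can be recorded as CR, CRh or the count part of PR. Each such patient moves a category by 5.0 points at n=20 or 4.3 at n=23; a smaller analysis set would make the shift larger. This assumes that supported counts occur at a response assessment, which the documents allow but do not quantify.

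Two stronger readings are tempting. One is that ORR is inflated. It is not, because CRi counts towards ORR and PR does not. The other is that haematological recovery is in fact overstated, or varies between sites with supportive care. The documents show only that it can be overstated: they identify no affected patient and give no site-level data. No error rate or sample-size figure is involved.

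**What to change.** In Appendix D and SAP 12.1:

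1. Require that the platelet count and ANC used for CR, CRh and PR are not supported by platelet transfusion or growth factor within a prespecified prior interval. The sponsor sets the interval; the documents give no basis for a particular length. Derive it from the dated transfusion and concomitant-medication records (Protocol 5.3.19 and 6.9.1).
2. Extend the CRi wording so that a patient with marrow blasts below 5% who otherwise meets CR or CRh, but only on supported counts, is CRi. Without this sentence the patient could fall to MLFS and alter RFS or EFS.
3. State that a patient who meets PR only on supported counts is not PR.
4. Apply the rule in the IDH-mutants cohort and, where dated records exist, in Part 1 and the all-comers cohort. Otherwise present it there as a sensitivity tabulation and state the difference wherever cohorts are combined.

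The cost is a few sentences and one derivation, plus a check of what the earlier records contain. The downside is that CR, CRh or PR figures may be slightly less favourable.
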